9.2.2.1 Visit 1; Baseline Visit

Upon patient enrolment, the following available data will be recorded on the patient's e-CRF.

- Visit date
- Diagnosis: date of the diagnosis of T2DM, Family history of T2DM
- Inclusion / Exclusion criteria

- Informed consent form: Date of Informed consent
- Demographic data: Age, gender,
- Diabetes mellitus related complication (Retinopathy, Neuropathy, Nephropathy)
- Medical history: Hypertension, Dyslipidaemia, Coronary artery disease, Stroke, Liver disease, Renal failure, Renal Transplant, Renal Stones Nephropathy, Prostate Diseases, Pancreatitis, Diabetic ketoacidosis, Surgery, Infections (other than UTIs) and heart diseases, other (history of concomitant disease within 6 months). In addition, genital defects, urinary tract anatomical defects, when available.
- Baseline lab variables when available – Complete Blood Count (CBC), Oral Glucose Tolerance Test (OGTT), ketones level, amylase, lipase, arterial blood gas, pH, bicarbonate, lipid profile tests, Blood Urea Nitrogen (BUN), liver tests, International Normalized Ratio (INR) for prothrombin time and platelets
- Physical examination: body mass index (BMI), blood pressure, pulse rate, weight
- Baseline HbA1C, blood glucose level (if available)
- Renal Function: record Serum creatinine, eGFR, urine ACR if results are available (collected within the latest 2month period) (if available)
- Concomitant anti-hyperglycemic agent: record any anti-hyperglycemic agents have been taken prior to the baseline visit (within 6 months prior to baseline)
- Concomitant medications: record all medications have been taken at least once since one month prior to the baseline visit.
- Dose of Empagliflozin / DPP4-Inhibitor given
- PASS physician's electronic signature for data integrity

At visit 1, the patient will be requested to contact the treating physician in the event of any adverse events noted after initiating Empagliflozin or the comparator DPP-4 inhibitor treatment.

9.2.2.2 Visit 2; 16±2 weeks from Visit 1

After 16±2 weeks from Visit 1, the patients will return for follow-up. The followings will be noted and recorded in the e-CRF.

- Visit date
- Physical examination: blood pressure, pulse rate, weight (if available)
- HbA1C (if available)
- Any change of Empagliflozin or comparator DPP-4 inhibitor given
- Concomitant anti-hyperglycemic agent including new medications taken since last visit: any change in the concomitant medications (dose and dosing intervals)

- Concomitant medications including new medications taken since last visit: any change in the concomitant medications (dose and dosing intervals)
- Any adverse events noted
- Study completion status
- Discontinuation or continuation (if interruption, date of last administration, reason for interruption)
- PASS physician's electronic signature for data integrity

9.2.2.3 Visit 3; 32±2 weeks from Visit 1

After 32±2 weeks from Visit 1, the patients will return for follow-up. The followings will be noted and recorded in the e-CRF.

- Visit date
- Physical examination: blood pressure, pulse rate, weight (if available)
- HbA1C (if available)
- Any change of Empagliflozin or comparator DPP-4 inhibitor given
- Concomitant anti-hyperglycaemic agent including new medications taken since last visit: any change in the concomitant medications (dose and dosing intervals)
- Concomitant medications including new medications taken since last visit: any change in the concomitant medications (dose and dosing intervals)
- Any adverse events noted
- Study completion status
- Discontinuation or continuation (if interruption, date of last administration, reason for interruption)
- PASS physician's electronic signature for data integrity

9.2.2.4 Visit 4; 52 weeks End of study

- Visit date
- Physical examination: blood pressure, pulse rate, weight
- HbA1C (if available)
- Any change of Empagliflozin or comparator DPP-4 inhibitor given
- Concomitant anti-hyperglycaemic agent including new medications taken since last visit : any change in the concomitant medications (dose and dosing intervals)
- Concomitant medications including new medications taken since last visit : any change in the concomitant medications (dose and dosing intervals)
- Any adverse events noted
- Discontinuation or continuation (if interruption, date of last administration, reason for interruption)

- PASS physician's electronic signature for data integrity

9.2.2.5 Follow-up period

Follow-up will start the day after the index date and last until end of study data (date of death or date of study end), the date during follow-up when specific exclusion criteria are met, the end date of the treatment of the index drug (Empagliflozin or other SGLT2 inhibitor or DPP-4 inhibitor) plus a defined grace period (30 days after the end of the last prescription's supply in main analyses), or the date on which a new treatment episode starts with any of the other index drugs.

Patients with adverse events noted at the final follow-up visit or upon premature discontinuation of Empagliflozin or the comparator DPP-4 inhibitor will be monitored further until the resolution of those adverse events. Alternatively, those patients will be followed up until the PASS physician and sponsor agree that no further follow-up is necessary.

9.2.3 Study discontinuation

Boehringer Ingelheim reserves the right to discontinue the study overall or at a particular study site at any time for the following reasons:

1. Failure to meet expected enrolment goals overall or at a particular study site
2. Emergence of any efficacy/safety information that could significantly affect continuation of the study, or any other administrative reasons.
3. Violation of Good Clinical Practice (GCP) (as applicable), the study protocol, or the contract by a study site or investigator, disturbing the appropriate conduct of the study

The investigator / the study site will be reimbursed for reasonable expenses incurred in case of study termination (except in case of the third reason).

9.3 VARIABLES

9.3.1 Safety

9.3.1.1 Outcomes of safety

All reported adverse events in patients who take at least one dose of Empagliflozin or comparator DPP-4 inhibitor will be reported.

All documented information in the e-CRF will be analyzed at the end of the study. At the time of analysis, safety outcomes will be analyzed based on the current versions of MedDRA & BICMQs

9.3.2 Exposures

The definition of drug exposure for Empagliflozin will be any patient using at least one prescription of Empagliflozin tablets (10 or 25 mg) or fixed-dose combinations with metformin. For the comparator group, the patients will have at least one prescription of DPP-4 inhibitors. DPP-4 inhibitor users included in this study will be using one of the following approved drugs in Saudi Arabia: Sitagliptin, Saxagliptin, Vildagliptin, Alogliptin, Linagliptin, or fixed-dose combinations of these drugs with metformin. [R17-3427]

Furthermore, each member of the population exposed to Empagliflozin must have at least one prescription for Empagliflozin, with or without other glucose-lowering drugs (GLDs), and have no prior prescriptions of a DPP-4 inhibitor or Empagliflozin during the available pre-index period. Each member of the population exposed to a DPP-4 inhibitor must have at least one prescription for a DPP-4 inhibitor, with or without other GLDs, and no prior prescriptions of a DPP-4 inhibitor or Empagliflozin during the available pre-index period.

Add-on therapy will be allowed after using the exposure of interest as the initial drug for new users. Therefore, using the drug as part of dual therapy or triple therapy will be allowed.

The use of studied medications will be defined on different levels: current use, recent use and discontinuation of the studied drugs. Current use of the index drugs will be defined from the date of prescription of Empagliflozin or DPP-4 inhibitor to the end of supply for that prescription plus a period of 30 days. Recent use will be defined from the end of current use (30 days after end of supply) until 90 days later (which is 120 days after end of supply).

Discontinuation of the index drug will be defined as no further prescription 120 or more days after the end of the last prescription's supply. Patients who discontinue an index drug and then subsequently initiate another index drug will not be allowed to re-enter the study.

Patients switching to or adding Empagliflozin to other antidiabetic medications will be compared to patients switching to or adding comparator treatment on the same background therapy. Identification of a "new-user" design is an appropriate method for studying second-line therapies in chronic conditions.

During the statistical analyses, analyses will be stratified by treatment complexity (mono vs. dual vs. triple therapy) and by calendar time of treatment initiation. Prior or current use of insulin is allowed; an additional stratified analysis by insulin use is planned. Propensity scores based on information prior to the index date will be used to account for potential confounding.

9.3.3 Outcomes

This study proposed to assess and evaluate the risk of ketoacidosis, severe urinary tract infections, volume depletion and dehydration associated with the use of Empagliflozin compared with the use of DPP-4 inhibitors in T2DM. As per ADA, ketoacidosis is defined as a serious condition because of inability of body cells to get glucose as a source of energy, and subsequently, the body produces ketones as the result of burning fat for energy. DKA occurs because of a lack of insulin in the body, not enough food intakes in diabetic patients and insulin reaction (low blood glucose). It is characterized by high ketones levels, positive ketones in the urine and high pH levels. Specifically, for the SGLT2i induced DKA the blood glucose level may not be increased above 240 mg/dl. [R17-3411] –The second outcome, which is severe urinary tract infection, is defined as pyelonephritis or urosepsis. Volume

depletion is the reduction in the extracellular fluids. This differs from dehydration, which is the loss of total body water that leads to hypertonicity. To ascertain the outcome diagnosis, signs and symptoms along with the laboratory tests results will be used.

All identified primary outcomes will be evaluated also during the period of the month of Ramadan.

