11.2 ADVERSE EVENT AND SERIOUS ADVERSE EVENT COLLECTION AND REPORTING

The investigator shall maintain and keep detailed records of all AEs in their patient files.

Collection of AEs

The study design is of non-interventional nature and the study is conducted within the conditions of the approved marketing authorization.

The following must be collected by the investigator in the e-CRF from signing the informed consent onwards until the end of the study:

- All adverse events

All AEs, including those persisting after study completion must be followed up until they are resolved, have been sufficiently characterized, or no further information can be obtained.

The investigator carefully assesses whether an AE constitutes an ADR using the information below.

AEs considered “Always Serious”

In accordance with the European Medicines Agency initiative on Important Medical Events, BI has set up a list of AEs, which by their nature, can always be considered to be “serious” even though they may not have met the criteria of an SAE as given above.

The latest list of “Always Serious AEs” can be found in the ISF. These events should always be reported in the eCRF as SAEs as described above.

Note: Cancers of new histology and exacerbations of existing cancer must be reported as a serious event regardless of the duration between discontinuation of the drug and the occurrence of the cancer.

Causal relationship of adverse event

The definition of an adverse reaction implies at least a reasonable possibility of a causal relationship between a suspected medicinal product and an adverse event. An adverse reaction, in contrast to an adverse event, is characterized by the fact that a causal relationship between a medicinal product and an occurrence is suspected.

Medical judgment should be used to determine the relationship, considering all relevant factors, including pattern of reaction, temporal relationship, de-challenge or re-challenge, confounding factors such as concomitant medication, concomitant diseases and relevant history.

Arguments that may suggest a **reasonable causal relationship** could be:

- The event is **consistent with the known pharmacology** of the drug
- The event is known to be caused by or **attributed to the drug class**.

- A **plausible time to onset of the event** relative to the time of drug exposure.
- Evidence that the **event is reproducible** when the drug is re-introduced

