The following must be reported by the investigator on the NIS AE form from signing the informed consent onwards until the end of the study:

Type of Report	Timeline
All Serious Related Adverse Events (SAEs) with Jardiance® , Trajenta® and/or Synjardy®	immediately within 24 hours
Adverse Event of Special interest associated with Jardiance®	immediately within 24 hours
All AEs with fatal outcome in patients exposed to Jardiance®, Trajenta® and/or Synjardy®	immediately within 24 hours
All non-serious Related Adverse Events associated with Jardiance®, Trajenta® and/or Synjardy®	7 calendar days
All pregnancy associated with Jardiance®, Trajenta® and/or Synjardy® on pregnancy monitoring forms	7 calendar days

The same timelines apply if follow-up information becomes available for the respective events. In specific occasions the Investigator could inform the Sponsor upfront via telephone. This does not replace the requirement to complete and secure email or fax the NIS AE form.

Reporting of DKA cases:

An additional information will be requested with a targeted form.

Information required

For each reportable adverse event, the investigator should provide the information requested on the appropriate e-CRF pages and the NIS AE form.

Reporting of related Adverse Events associated with any other BI drug

The investigator is encouraged to report all adverse events related to any BI drug other than **Jardiance®, Trajenta® and/or Synjardy®** according to the local regulatory requirements for spontaneous AE reporting at the investigator's discretion by using the locally established routes and AE report forms. The term AE includes drug exposure during pregnancy, and, regardless of whether an AE occurred or not, any abuse, off-label use, misuse, medication error, occupational exposure, lack of effect, and unexpected benefit.

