2.1 Primary objective

The primary objective of this study is to estimate the incidence of

- Ketoacidosis
- Severe urinary tract infections (UTI)
- Volume depletion
- Dehydration

in T2DM patients initiating EMPAGLIFLOZIN compared with the incidence in T2DM patients initiating DPP-4 inhibitors.

The respective primary endpoints are incidences and occurrences of ketoacidosis, severe UTI, volume depletion and dehydration recorded as part of adverse event reporting and encoded according to MedDRA as defined in the Data Management Plan.

Statistical Analysis Plan (SAP)

Document Date: 17APR2019

Document Version: 1.0 Final

[figure not shown]

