4.7.5 Ketoacidosis, severe UTI, depletion and dehydration

As main endpoints, ketoacidosis, severe UTI (namely pyelonephritis and urosepsis), volume depletion and dehydration, will be derived from corresponding AE reporting. Crude and treatment-adjusted incidence rates will be presented by group and period, together with incidence rate ratios of EMPAGLIFLOZIN relative to DPP-4 inhibitor, as point estimates and with 95% confidence limits. Treatment-adjusted incidence rates are defined as crude incidence rates per 1,000 person-years. Per group, and, where appropriate, per stratum and/or subgroup, the number of person-years is the sum of length of index periods of all respective patients.

For each endpoint, the time from index date to first occurrence in days is determined. If the endpoint does not occur for a patient, the time is right-censored by the duration of the respective period, index period or follow-up period. By group, times to first occurrence will be described by means of Kaplan-Meier estimates with 95% confidence limits and, where appropriate, median times with 95% confidence limits.

Crude and treatment-adjusted incidence rates and respective incidence rate ratios will be described in summary tables by group and period, and per period in subgroups by metformin status, GLD status and insulin status, respectively. Ratios are defined as Empagliflozin to DPP-4 inhibitors.

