4.8 Handling of Missing Data

Data will be analyzed as reported. Missing data will not be replaced or imputed. Outlying values, if confirmed by site on data clarification, will be analyzed as reported.

Note that if specific endpoints (AEs i.e. ketoacidosis, volume depletion, dehydration serious UTI) are not reported for a patient in the AE section of the CRF it will be assumed that they did not experience that event.

Statistical Analysis Plan (SAP)

Document Date: 17APR2019

Document Version: 1.0 Final

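### The ketoacidosis description warns of cases without markedly raised glucose only for SGLT2 inhibitor patients, so comparator cases of that kind may be recognised less often.

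*Protocol*

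**What the plan says.** Ketoacidosis is one of four primary outcomes whose incidence is compared between new users of empagliflozin and of DPP-4 inhibitors (Protocol 8.1, SAP 2.1).

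Protocol 9.3.3 describes it for all patients by ketones and pH: "It is characterized by high ketones levels, positive ketones in the urine and high pH levels". It then adds one sentence about glucose: "Specifically, for the SGLT2i induced DKA the blood glucose level may not be increased above 240 mg/dl". Both sentences recur in Protocol 11.1, Table 1, which is presented as a table of clinical criteria with a column for definitions. On diagnosis in general, 9.3.3 says: "To ascertain the outcome diagnosis, signs and symptoms along with the laboratory tests results will be used". It gives no cut-off for ketones, pH, bicarbonate or glucose.

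The SAP takes the endpoint from adverse event reports. Section 2.1 has the events "recorded as part of adverse event reporting and encoded according to MedDRA as defined in the Data Management Plan", and 4.7.5 says that the main endpoints "will be derived from corresponding AE reporting". Under SAP 4.8, if the specific endpoints "are not reported for a patient in the AE section of the CRF it will be assumed that they did not experience that event".

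On collection, Protocol 11.2 states: "The following must be collected by the investigator in the e-CRF from signing the informed consent onwards until the end of the study", and the item listed is all adverse events, in either cohort. In the expedited-reporting table (Table 2), other rows name three products, but the row with a 24-hour limit for "Adverse Event of Special interest associated with Jardiance" names one. Below that table, a targeted form is announced for DKA cases. Its content, and whether it applies to both cohorts, are not stated.

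**The concern.** A comparative safety outcome should be described in terms that depend neither on the exposure nor on a judgement of its cause. Here the only number in the ketoacidosis description belongs to cases attributed to one of the two drug classes compared. The liver and renal rows of Table 1, by contrast, give numeric criteria that name no drug.

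The physician chooses the drug and nothing is blinded (Protocol 9, SAP 4.3). An investigator who reads the sentence is prompted to think of ketoacidosis in an empagliflozin patient whose glucose is not markedly raised, and gets no such prompt for a DPP-4 inhibitor patient. A comparator case that is not recognised is not reported as ketoacidosis, and SAP 4.8 then makes it a non-event.

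At stake is the ketoacidosis IRR. Propensity scores use information up to and including the index date (SAP 4.1), so they cannot correct unequal recognition of events during follow-up. The asymmetry might not be visible afterwards either: the SAP visit schedule (Table 3-1) lists blood glucose and other laboratory tests at Visit 1 only, where available, so values at the time of an event are not assured.

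**Working it through.** The plan gives no figure to reproduce. The 1,500 patients (750 per group) are a regulatory requirement (Protocol 9.5, SAP 4.2), with no assumed ketoacidosis rate or effect size.

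**Step 1: what the text requires of each cohort.**
- Glucose requirement for DPP-4 inhibitor patients: none in 9.3.3 or Table 1.
- Glucose requirement for empagliflozin patients: none. In its natural sense the sentence is permissive; it says what may be seen.
- General causes, with no drug named: lack of insulin, insufficient food intake, and an insulin reaction with low blood glucose.
- Counting rule: the same adverse event route for both cohorts (SAP 2.1, 4.7.5; Protocol 11.2).

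The formal criteria do not differ. The prompt given to the investigator does.

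**Step 2: direction.** If the prompt has any effect, lower-glucose cases are recognised relatively more often under empagliflozin than under a DPP-4 inhibitor. That lowers the observed comparator rate relative to the empagliflozin rate and raises the IRR. The expedited-reporting row for Jardiance alone draws attention to the same cohort.

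**Step 3: size, on assumed inputs.** Neither input is in the documents:
- f = share of ketoacidosis cases with glucose at or below 240 mg/dl;
- m = share of those cases that is missed in the comparator cohort and not in the empagliflozin cohort.

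If the true comparator rate is R, the observed rate is R × (1 − f·m). With a true IRR of 1 and full recognition under empagliflozin,

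observed IRR = R / [R × (1 − f·m)] = 1/(1 − f·m).

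| f | m = 0 | m = 50% | m = 100% |
|---|---|---|---|
| 5% | 1.00 | 1/0.975 = 1.03 | 1/0.95 = 1.05 |
| 10% | 1.00 | 1/0.95 = 1.05 | 1/0.90 = 1.11 |
| 20% | 1.00 | 1/0.90 = 1.11 | 1/0.80 = 1.25 |
| 30% | 1.00 | 1/0.85 = 1.18 | 1/0.70 = 1.43 |

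The last column is an upper bound for each f, because every lower-glucose comparator case is then lost.

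**Step 4: small counts.** Protocol 9.9 concedes that there may be too few patients to assess DKA. With few events a single missed case matters: if the comparator cohort had two true cases and one was missed, its rate would halve and the IRR would double (2/1 = 2).

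**The case against.** The strongest reply is that the sentence changes nothing. No patient needs a raised glucose to count, so there is no requirement to relax. The same paragraph names low blood glucose among the general causes, so ketoacidosis without hyperglycaemia is already contemplated for both cohorts. All adverse events are collected in both, whatever their cause. The Data Management Plan, the targeted DKA form and the sponsor's MedDRA queries are not among the documents reviewed and may hold further criteria. The expected loss is also small in absolute terms. Assume 1 to 5 comparator cases per 1,000 person-years over at most 750 person-years, that is 0.75 to 3.75 cases. With f from 10% to 30% and m = 100%, the loss is 0.75 × 0.10 ≈ 0.08 to 3.75 × 0.30 ≈ 1.1 cases.

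Much of this stands, and it rules out three stronger readings that a reader might infer:
- **Different case criteria in the two cohorts.** This needs a glucose requirement for DPP-4 inhibitor patients, and none is written.
- **An upper limit that excludes empagliflozin cases above 240 mg/dl, biasing the IRR downward.** In context the sentence cautions about presentation; nothing turns it into an exclusion rule.
- **Counting that depends on causal attribution.** The reference to SGLT2i-induced cases qualifies only the glucose remark; the SAP counts coded adverse events in either cohort.

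What the reply does not answer is recognition. Collecting all adverse events captures ketoacidosis only where the investigator identifies it, and the text draws attention to the less obvious presentation in one cohort only.

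**Conclusion.** The point holds as a risk of unequal recognition, running in one direction. If the wording affects what investigators recognise, the ketoacidosis IRR is biased upward, against empagliflozin. The size cannot be derived from the documents. On the assumed inputs it runs from none (m = 0) to 1.43 (f = 30%, m = 100%), with values of 1.03 to 1.18 when half of the lower-glucose comparator cases are missed. These figures assume a true IRR of 1 and no corresponding loss under empagliflozin. With very few events the estimate will be imprecise in any case. The reason to act is that this source of bias is avoidable and cheap to remove, and that the planned propensity analysis cannot correct it.

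**What to change.** 1. In Protocol 9.3.3 and Table 1, reword the glucose sentence so that it names no drug and no attributed cause and applies identically to both cohorts. Its clinical content is for the sponsor to settle.
2. In Protocol 11.2, state that the targeted DKA form is used for every reported case in both cohorts, and that it records glucose and ketones at the time of the event where measured.
3. In SAP 4.7.5, add a descriptive table of ketoacidosis cases per cohort by glucose at or below versus above 240 mg/dl, with a category for not measured.

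Rewording does not by itself supply the missing cut-offs, so some unequal recognition could remain; items 2 and 3 make it possible to look for it.

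Cost: a protocol amendment, which needs ethics committee and authority approval (Protocol 10.1), a SAP update, one small table, and a few more comparator reports to process. Protocol version 3.0 is dated 23 September 2019 and plans the last patient in for Q4 2019, so cases reported before the change will have been collected under the present wording. The study report should say so.
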